2. ABBREVIATIONS

Abbreviations pertain to the Statistical Analysis Plan (SAP) only (not the tables, figures and listings [TFLs]).

AE	Adverse event
ADA	Anti-drug antibody
ALP	Alkaline phosphatase
ALT	Alanine aminotransferase
AUC	Area under the concentration versus time curve
AUC(0-∞)	Area under the concentration versus time curve from time zero to infinity
AUC(0- τ)	Area under the concentration versus time curve during one dosing interval
AUC(0- t_{last})	Area under the concentration versus time curve from time zero to time t , where t is the last time point with a measurable concentration
%AUC(t_{last} -∞)	Percentage of AUC(0-∞) extrapolated
BQL	Below the lower limit of quantitation
C_{last}	Last quantifiable drug concentration
C_{max}	Maximum observed drug concentration
CI	Confidence interval
CL/F	Apparent total body clearance of drug calculated after extra-vascular administration
CRF	Case Report Form
CRU	Clinical Research Unit
CSR	Clinical Study Report
CV	Coefficient of variation
ECG	Electrocardiogram
EE	Ethinyl Estradiol
GE	Gastric emptying
ICH	International Conference on Harmonisation
LLOQ	Lower limit of quantification
LS	Least square
MedDRA	Medical Dictionary for Regulatory Activities
MRE	Magnetic resonance elastography

NGM	Norgestimate
NGMN	Norelgestromin
OC	Oral contraceptive
PG	Plasma glucose
PK	Pharmacokinetic(s)
SAP	Statistical Analysis Plan
SC	Subcutaneous
SD	Standard deviation
TBL	Total bilirubin
TE ADA	Treatment-emergent antidrug antibody
TFLs	Tables, Figures, and Listings
$t_{\frac{1}{2}}$	Half-life associated with the terminal rate constant (λ_z) in non-compartmental analysis
t_{\max}	Time of maximum observed drug concentration
ULN	Upper limit of normal
V_z/F	Apparent volume of distribution during the terminal phase after extra-vascular administration
V_{ss}/F	Apparent volume of distribution at steady state after extra-vascular administration
WHO	World Health Organization

3. INTRODUCTION

This SAP has been developed after review of the Clinical Study Protocol (final version dated 18 October 2019) and Protocol Amendment (a) (final version dated 06 December 2019).

This SAP describes the planned analysis of the safety, tolerability and pharmacokinetic (PK) data from this study. A detailed description of the planned TFLs to be presented in the clinical study report (CSR) is provided in the accompanying TFL shell document.

The intent of this document is to provide guidance for the statistical and PK analyses of data. In general, the analyses are based on information from the protocol, unless they have been modified by agreement with Eli Lilly and Company. A limited amount of information concerning this study (e.g., objectives, study design) is given to help the reader's interpretation. For open-label studies, this SAP must be signed off prior to first subject visit for this study. When the SAP and TFL shells are agreed upon and finalized, they will serve as the template for this study's CSR.

This SAP supersedes the statistical considerations identified in the protocol; where considerations are substantially different, they will be so identified. If additional analyses are required to supplement the planned analyses described in this SAP, they may be performed and will be identified in the CSR. Any substantial deviations from this SAP will be agreed upon with Eli Lilly and Company and identified in the CSR. Any minor deviations from the TFLs may not be documented in the CSR.

This SAP is written with consideration of the recommendations outlined in the International Conference on Harmonisation (ICH) E9 Guideline entitled Guidance for Industry: Statistical Principles for Clinical Trials¹ and the ICH E3 Guideline entitled Guidance for Industry: Structure and Content of Clinical Study Reports².

4. STUDY OBJECTIVES

4.1 Primary

To evaluate the effect of a single subcutaneous (SC) dose of tirzepatide on the PK of a combination oral contraceptive (OC) in healthy female subjects.

4.2 Secondary

[figure not shown]
To evaluate the safety and tolerability of a single SC dose of tirzepatide when coadministered with an OC in healthy female subjects.

5. STUDY DESIGN

This is a single-center, open-label, 2-period, fixed sequence study with a lead-in period, in healthy female subjects. Subjects may already have been on OC medication prior to screening or be OC naïve. Potential subjects will be screened to assess their eligibility to enter the study within 28 days prior to Day 1 of the lead-in period. A final follow-up visit will occur on Day 49 ± 1 day (i.e. 28 days ± 1 day after tirzepatide dosing). During each treatment period, the PK of individual components of the OC combination will be assessed on Day 21 to enable evaluation

of OC PK alone. During period 2, tirzepatide will be administered on Day 20 such that peak exposure by Day 21 (tirzepatide time of maximum observed drug concentration [t_{max}] ~ 24 hours postdose) can be attained when OC PK is evaluated on Day 21 (norgestimate [NGM] and ethinyl estradiol [EE] are rapidly absorbed after oral administration). This will permit studying the influence of tirzepatide on OC PK, in the presence of maximum exposure; i.e. with greatest impact on gastric emptying (GE).

Figure GPGR.1 illustrates the study design.

Abbreviations: Adm = admission to the clinical research unit; CRU = clinical research unit; Dis = discharge from the clinical research unit; OC = oral contraceptive; PK = pharmacokinetic

Figure GPGR.1. Illustration of study design

6. TREATMENTS

The following is a list of the study treatment abbreviations that will be used in the TFLs.

Study Treatment Name	Abbreviation	Treatment order in TFL
0.035 mg EE / 0.25 mg NGM	OC	1
0.035 mg EE / 0.25 mg NGM + 5 mg tirzepatide SC	OC + 5 mg tirzepatide SC	2

7. SAMPLE SIZE JUSTIFICATION

Approximately 42 subjects will be enrolled so that a minimum of 28 subjects complete the study.

For EE area under the concentration versus time curve (AUC) and maximum observed drug concentration (C_{max}), the intra-subject variability (coefficient of variation [CV]) was estimated to be 18.2% and 14.2%, respectively (derived from study H9X-MC-GBCQ). Based on this assumption, 28 subjects will provide a precision of 0.10 and 0.08 on a log-scale for AUC and C_{max} , respectively. This would result in a 90% probability that the half-width of the 90% confidence interval (CI) of the ratio of geometric least square means for AUC and C_{max} is no larger than 9.3% and 7.3%, respectively.

For norelgestromin (NGMN) AUC and C_{max} , the intra-subject variability (CV) was estimated to be 16.3% and 20.0% respectively (derived from study H9X-MC-GBCQ). Based on this assumption, 28 subjects will provide a precision of 0.09 and 0.11 on a log-scale for AUC and C_{max} , respectively. This would result in a 90% probability that the half-width of the 90% CI of the ratio of the geometric least square means for AUC and C_{max} is no larger than 8.3% and 10.2%, respectively.

8. DEFINITION OF ANALYSIS POPULATIONS

The “Safety” population will consist of all subjects who received at least one dose of OC or tirzepatide, whether or not they completed all protocol requirements.

The “Pharmacokinetic” population will consist of all subjects who received at least one dose of OC or tirzepatide and have evaluable PK data.

All protocol deviations that occur during the study will be considered for their severity/impact and will be taken into consideration when subjects are assigned to analysis populations.

9. STATISTICAL METHODOLOGY

9.1 General

Data listings will be provided for all data that is databased. Summary statistics and statistical analysis will only be presented for data where detailed in this SAP. For continuous data, summary statistics will include the arithmetic mean, arithmetic standard deviation (SD), median, min, max and N; for log-normal data (e.g. the PK parameters: AUCs and C_{max}) the geometric mean and geometric CV% will also be presented. For categorical data, frequency count and percentages will be presented. Data listings will be provided for all subjects up to the point of withdrawal, with any subjects excluded from the relevant population highlighted. Summary statistics and statistical analyses will generally only be performed for subjects included in the relevant analysis population. For the calculation of summary statistics and statistical analysis, unrounded data will be used.

Mean change from baseline is the mean of all individual subjects' change from baseline values. Each individual change from baseline will be calculated by subtracting the individual subject's baseline value from the value at the timepoint. The individual subject's change from baseline

values will be used to calculate the mean change from baseline using a SAS procedure such as Proc Univariate.

Data analysis will be performed using SAS® Version 9.4 or greater.

9.2 Demographics and Subject Disposition

Subject disposition will be listed. The demographic variables age, race, ethnicity, body weight, height and body mass index will be summarized and listed.

All other demographic variables will be listed only.

9.3 Pharmacokinetic Assessment

9.3.1 Pharmacokinetic Analysis

PK parameter estimates will be determined using non-compartmental procedures in validated software program (Phoenix WinNonlin Version 8.1 or later).

Plasma concentrations of NGM, NGMN and EE will be used to determine the following PK parameters, when possible:

Parameter	Units	Definition
AUC(0- τ)	h*pg/mL	Area under the concentration versus time curve during one dosing interval
C _{max}	pg/mL	Maximum observed drug concentration
t _{max}	h	Time of maximum observed drug concentration
t _{1/2}	h	Half-life associated with the terminal rate constant (λ_z) in non-compartmental analysis
CL/F	L/h	Apparent total body clearance of drug calculated after extra-vascular administration
V _z /F	L	Apparent volume of distribution during the terminal phase after extra-vascular administration

Plasma concentrations of tirzepatide will be used to determine the following PK parameters, when possible:

Parameter	Units	Definition
AUC(0-t _{last})	h*ng/mL	Area under the concentration versus time curve from time zero to time t, where t is the last time point with a measurable concentration
AUC(0-∞)	h*ng/mL	Area under the concentration versus time curve from time zero to infinity
%AUC(t _{last} -∞)	%	Percentage of AUC(0-∞) extrapolated
C _{max}	ng/mL	Maximum observed drug concentration
t _{max}	h	Time of maximum observed drug concentration
t _{1/2}	h	Half-life associated with the terminal rate constant (λ_z) in non-compartmental analysis
CL/F	L/h	Apparent total body clearance of drug calculated after extra-vascular administration
V _{z/F}	L	Apparent volume of distribution during the terminal phase after extra-vascular administration
V _{ss/F}	L	Apparent volume of distribution at steady state after extra-vascular administration

Additional PK parameters may be calculated, as appropriate. Plasma concentrations of tirzepatide will be listed and summarized.

The software and version used for the final analyses will be specified in the CSR. Any exceptions or special handling of data will be clearly documented within the final study report.

Formatting of tables, figures and abbreviations will follow the Eli Lilly Global PK/PD/TS Tool: NON-COMPARTMENTAL PHARMACOKINETIC STYLE GUIDE. The version of the tool effective at the time of PK analysis will be followed.

General PK Parameter Rules

- Actual sampling times will be used in the final analyses of individual PK parameters, except for non-bolus pre-dose sampling times which will be set to zero. For non-bolus, multiple dose profiles, the pre-dose time will be set to zero unless a time deviation falls outside of the protocol blood collection time window which is considered to impact PK parameter derivation.
- C_{max} and t_{max} will be reported from observed values. If C_{max} occurs at more than one time point, t_{max} will be assigned to the first occurrence of C_{max}.
- AUC parameters will be calculated using a combination of the linear and logarithmic trapezoidal methods (linear-log trapezoidal rule). The linear trapezoidal method will be applied up to t_{max} and then the logarithmic trapezoidal method will be used after t_{max}. The minimum requirement for the calculation of AUC will be the inclusion of at least three consecutive concentrations above the lower limit of quantification (LLOQ), with at least one of these concentrations following C_{max}.

- AUC(0-∞) values where the percentage of the total area extrapolated is more than 20% will be flagged. Any AUC(0-∞) value excluded from summary statistics will be noted in the footnote of the summary table.
- Half-life ($t_{1/2}$) will be calculated, when appropriate, based on the apparent terminal log-linear portion of the concentration-time curve. The start of the terminal elimination phase for each subject will be defined by visual inspection and generally will be the first point at which there is no systematic deviation from the log-linear decline in plasma concentrations. Half-life will only be calculated when a reliable estimate for this parameter can be obtained comprising of at least 3 data points. If $t_{1/2}$ is estimated over a time window of less than 2 half-lives, the values will be flagged in the data listings. Any $t_{1/2}$ value excluded from summary statistics will be documented in the footnote of the summary table.
- A uniform weighting scheme will be used in the regression analysis of the terminal log-linear portion of the concentration-time curve.
- The parameters based on the predicted last quantifiable drug concentration (C_{last}) will be reported.

Individual PK Parameter Rules

- Only quantifiable concentrations will be used to calculate PK parameters with the exception of special handling of certain concentrations reported below the lower limit of quantitation (BQL). Plasma concentrations reported as BQL will be set to a value of zero when all of the following conditions are met:
 - The compound is non-endogenous.
 - The samples are from the initial dose period for a subject or from a subsequent dose period following a suitable wash-out period.
 - The time points occur before the first quantifiable concentration.
- All other BQL concentrations that do not meet the above criteria will be set to missing.
- Also, where two or more consecutive concentrations are BQL towards the end of a profile, the profile will be deemed to have terminated and therefore any further quantifiable concentrations will be set to missing for the calculation of the PK parameters unless it is considered to be a true characteristic of the profile of the drug.
- For multiple-dosing data, when pre-dose concentrations are missing, the value to be substituted will be C_{min} for the dosing interval.

Individual Concentration vs. Time Profiles

- Individual concentrations will be plotted utilizing actual sampling times.

- The terminal point selections will be indicated on a semi-logarithmic plot.

Average Concentration vs. Time Profiles

- The average concentration profiles will be graphed using scheduled (nominal) sampling times.
- The average concentration profiles will be graphed using arithmetic average concentrations.
- The pre-dose average concentration for single-dose data from non-endogenous compounds will be set to zero. Otherwise, only quantifiable concentrations will be used to calculate average concentrations.
- Concentrations at a sampling time exceeding the sampling time window specified in the protocol, or $\pm 10\%$, will be excluded from the average concentration profiles.
- Concentrations excluded from the mean calculation will be documented in the final study report.
- A concentration average will be plotted for a given sampling time only if 2/3 of the individual data at the time point have quantifiable measurements that are within the sampling time window specified in the protocol or $\pm 10\%$. An average concentration estimated with less than 2/3 but more than 3 data points may be displayed on the mean concentration plot if determined to be appropriate and will be documented within the final study report.

Treatment of Outliers during Pharmacokinetic Analysis

Application of this procedure to all PK analyses is not a requirement. Rather, this procedure provides justification for exclusion of data when scientifically appropriate. This procedure describes the methodology for identifying an individual value as an outlier for potential exclusion, but does not require that the value be excluded from analysis. The following methodology will not be used to exclude complete profiles from analysis.

Data within an Individual Profile

A value within an individual profile may be excluded from analysis if any of the following criteria are met:

- For PK profiles during single dosing of non-endogenous compounds, the concentration in a pre-dose sample is quantifiable.
- For any questionable datum that does not satisfy the above criteria, the profile will be evaluated and results reported with and without the suspected datum.

Data between Individual Profiles

1. If $n < 6$, then the dataset is too small to conduct a reliable range test. Data will be analyzed with and without the atypical value, and both sets of results will be reported.
2. If $n \geq 6$, then an objective outlier test will be used to compare the atypical value to other values included in that calculation:
 - a. Transform all values in the calculation to the logarithmic domain.
 - b. Find the most extreme value from the arithmetic mean of the log transformed values and exclude that value from the dataset.
 - c. Calculate the lower and upper bounds of the range defined by the arithmetic mean $\pm 3 \times \text{SD}$ of the remaining log-transformed values.
 - d. If the extreme value is within the range of arithmetic mean $\pm 3 \times \text{SD}$, then it is not an outlier and will be retained in the dataset.
 - e. If the extreme value is outside the range of arithmetic mean $\pm 3 \times \text{SD}$, then it is an outlier and will be excluded from analysis.

If the remaining dataset contains another atypical datum suspected to be an outlier and $n \geq 6$ following the exclusion, then repeat step 2 above. This evaluation may be repeated as many times as necessary, excluding only one suspected outlier in each iteration, until all data remaining in the dataset fall within the range of arithmetic mean $\pm 3 \times \text{SD}$ of the log-transformed values.

Reporting of Excluded Values

Individual values excluded as outliers will be documented in the final report. Approval of the final report will connote approval of the exclusion.

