9.3.2 Pharmacokinetic Statistical Methodology

PK parameters will be evaluated to estimate the effect of tirzepatide on the PK of OC (NGM, NGMN and EE); OC administered alone will be the reference treatment and OC coadministered with tirzepatide will be the test treatment. Log-transformed $\text{AUC}(0-\tau)$ and C_{max} of NGM, NGMN and EE will be analyzed using a paired t-test. The treatment differences between the test and reference arm will be back-transformed to present the ratio of geometric means, corresponding 90% CI, and p-value from the paired t-test.

Example SAS code:

```
proc ttest data=<data in> alpha=0.1;
  by analyte param;
  paired test*ref;
run;
```

The t_{max} will be analyzed using a Wilcoxon signed rank test for the same comparison. Estimates of the median of differences, the 90% CI for the median of differences, and p-value from the Wilcoxon signed rank test will be calculated.

The PK parameters for each treatment and analyte will be summarised and listed. Furthermore, the geometric mean and 90% CI of $AUC(0-\tau)$ and C_{max} of NGM, NGMN and EE will be plotted, along with the individual values, against treatment. For t_{max} , the median and individual values will be plotted against treatment.

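### BQL rule for the Day 21 contraceptive profiles can replace a BQL trough by a quantifiable Cmin, inflating AUC(0-τ) and raising its ratio mainly when the first quantifiable sample comes later with tirzepatide

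*SAP*

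**What the plan says.** SAP 9.3.1, Individual PK Parameter Rules, starts from this principle: "Only quantifiable concentrations will be used to calculate PK parameters with the exception of special handling" of certain BQL values. A BQL value becomes zero only if three conditions all hold: the compound is non-endogenous, the time point precedes the first quantifiable concentration, and "The samples are from the initial dose period for a subject or from a subsequent dose period following a suitable wash-out period". For the rest, "All other BQL concentrations that do not meet the above criteria will be set to missing". For multiple-dosing data, "when pre-dose concentrations are missing, the value to be substituted will be C_{min} for the dosing interval".

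The General PK Parameter Rules apply the linear trapezoid up to tmax and the logarithmic one after it. They also state that "C_{max} and t_{max} will be reported from observed values".

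Section 5 places the contraceptive profiles on Day 21 of each treatment period, after a lead-in. Sections 9.4.1 and 9.4.5 show that the contraceptive is already taken in the lead-in. Section 9.3.2 carries the result into the primary comparison: log-transformed AUC(0-τ) and "C_{max} of NGM, NGMN and EE will be analyzed using a paired t-test".

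**The concern.** A trough measured below the LLOQ is known to be low. The literal rule chain discards that knowledge and puts a value at or above the LLOQ at time 0, because Cmin is taken from quantifiable values only. Any further BQL samples before the rise are deleted, so one straight line runs from Cmin to the first quantifiable sample, over time in which the drug was measured as BQL.

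The error grows with the time to the first quantifiable sample. Section 5 times tirzepatide so that its effect on gastric emptying is greatest when the contraceptive is profiled, so any delay would fall in the test period only. The error need not cancel in the paired ratio and could partly mask a fall in exposure.

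The rule is also open to more than one reading. The SAP does not say what counts as an initial dose period or a suitable wash-out for the contraceptive cycles, or whether a BQL value set to missing is a missing pre-dose sample for the Cmin rule.

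**Working it through.** **1. The plan's own precision, for scale.** SAP Section 7 gives 28 completers and AUC CVs of 18.2% (EE) and 16.3% (NGMN). With σ = √ln(1+CV²), the log half-width at 90% assurance is t(0.95,27) × σ × √(2/28) × √(χ²(0.90,27)/27). This gives 0.096 and 0.086, which round to the stated 0.10 and 0.09. With the normal quantile in place of t, half the distance between the back-transformed limits is 9.27% and 8.31%, matching the stated 9.3% and 8.3%. The SAP has no figure for the BQL rule itself.

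**2. Algebra.** Let t_k be the first quantifiable time, C_k its concentration and t_(k-1) the sample before it.
- Leading BQL set to zero: leading area = 0.5 × (t_k − t_(k-1)) × C_k.
- Literal rule: leading area = 0.5 × t_k × (Cmin + C_k).
- Excess of the literal rule = 0.5 × t_k × Cmin + 0.5 × t_(k-1) × C_k.

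The second term is zero if the first post-dose sample is quantifiable, and dominates when it is not.

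**3. One worked case (all inputs assumed).** One compartment at steady state, ka 2/h, ke 0.3/h (half-life 2.3 h), τ 24 h, dose/volume 1; samples at 0, 0.5, 1, 1.5, 2, 3, 4, 6, 8, 12, 16 and 24 h; LLOQ 5% of reference Cmax (0.0358); true ratio 1.00; test lag 1.0 h.
- Reference: t_k = 0.5, t_(k-1) = 0, Cmin = 0.1068. Excess = 0.5 × 0.5 × 0.1068 = 0.0267. AUC goes from 3.2862 (zero) to 3.3129.
- Test: t_k = 1.5, t_(k-1) = 1.0, C_k = 0.5806, Cmin = 0.0434. Excess = 0.5 × 1.5 × 0.0434 + 0.5 × 1.0 × 0.5806 = 0.3229. AUC goes from 3.2722 to 3.5951.
- Ratio: 3.5951/3.3129 = 1.085 under the literal rule; 3.2722/3.2862 = 0.996 with zeros.

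**4. Grid.** Same model and samples, four half-lives, LLOQ at 1, 2, 5, 10 or 20% of reference Cmax. The trough is BQL in 9 of 20 cells; the other 11 show no effect. Ratios under the literal rule (true ratio 1.00):

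| Half-life | LLOQ with BQL trough | Lag 1.0 h | Lag 1.6 h |
|---|---|---|---|
| 2.3 h | 1–20% | 1.085–1.128 | 1.114–1.155 |
| 4.6 h | 5–20% | 1.050–1.058 | 1.068–1.081 |
| 6.9 h | 20% | 1.037 | 1.051 |
| 11.6 h | none | no effect | no effect |

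Over the 27 combinations of these 9 cells with lags of 0.6, 1.0 and 1.6 h, the literal rule gives 1.020–1.155, zero gives 0.981–1.009 and LLOQ/2 gives 0.994–1.026. Both alternatives are closer to 1.00 in all 27.

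**5. No lag.** A wider grid varied absorption, elimination, bioavailability and LLOQ, with troughs BQL in both periods. Shift in the ratio against zero handling:
- First post-dose sample quantifiable in both periods: median about 0; range −1.3 to +1.9% with that sample at 0.25 h, −4.4 to +3.7% at 0.5 h, −10.1 to +7.7% at 1 h.
- Slower absorption alone leaves the first test sample BQL: −4.9 to +8.6%.

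The Cmin term cancels in the ratio only if Cmin relative to AUC is the same in both periods.

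**6. Other readings of the text.**
- Both periods count as washed out: zeros in both, and this bias disappears.
- Only Period 1 counts as the initial dose period: zeros in Period 1, Cmin in Period 2. The ratio rises by 0.2 to 1.3% in the base cases without a lag.
- A BQL trough is not a missing sample for the Cmin rule, so the area starts at the first quantifiable sample: 0.982–0.998 at lags of 1.0 to 1.6 h, which is 5 to 16 points below the literal chain on the same data.

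**7. Cohort.** One affected subject of 28 moves the geometric mean ratio by exp(ln 1.037/28) − 1 = 0.13% up to exp(ln 1.155/28) − 1 = 0.52%. A 1% shift needs 28 × ln 1.01/ln 1.155 = 1.9, so 2 subjects, up to 28 × ln 1.01/ln 1.037 = 7.7, so 8 subjects.

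**The case against.** The trigger rests on facts that are not in the SAP. It gives no LLOQ, trough, contraceptive half-life or sampling times, and some of these normally sit in the protocol or assay report. If every trough is quantifiable, the chain never starts. Section 5 supports an effect on gastric emptying, but not an absorption lag of any particular length. Even where a profile is affected, a single subject moves the result little against planned half-widths of 8.3% to 9.3%. On-treatment troughs are not truly zero, so declining to impute zero is defensible. Section 9.3.1 also requires special handling to be documented, and asks for results with and without a questionable value.

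Most of this stands, and it limits the point to a conditional one. Two stronger readings should be resisted. A reader might infer that the trial's AUC(0-τ) ratio is biased upward and hides a fall in exposure. The SAP does not support that: the frequency is unknown, and the direction depends on terms it leaves undefined. A reader might also infer that the ratio moves only if tirzepatide causes a lag. Step 5 of the working shows shifts without one, in either direction.

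What does not stand is that the existing clauses settle the matter. They disclose what was done but do not say which BQL rule applies to these profiles.

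**Conclusion.** The point holds as a conditional weakness in a stated rule. The size depends on the assumed model, sampling times and LLOQ, so the figures of about +4% to +16% per affected profile show what the rule can do, not what it will do here. A cohort effect comparable with the planned precision would need many affected subjects, and nothing in the SAP shows that there will be any. Cmax and tmax are untouched because they are taken from observed values.

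The ambiguity is firmer than the bias: defensible readings of the same text give different AUC(0-τ) values in the primary comparison, and one of them treats the two periods differently. This is worth an inexpensive clarification. It is not a flaw that undermines the analysis.

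**What to change.** For the Day 21 NGM, NGMN and EE profiles, state one identical rule for both periods:
- BQL samples at pre-dose and before the first quantifiable post-dose sample stay in the AUC calculation at zero, with LLOQ/2 as a sensitivity analysis.
- Cmin substitution applies only to pre-dose samples that were not collected or not reportable. A BQL result is not a missing sample for this purpose.
- The report gives the number of affected profiles by analyte and period.

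Cost: two lines of SAP wording, one data-handling setting, one repeat run for the sensitivity analysis and one count. Downside: neither value is best everywhere. Zero reads slightly low when the trough lies just below the LLOQ (down to 0.981 in the illustration), and LLOQ/2 reads slightly high when the trough is far below it (up to 1.026). Reporting both shows whether the choice matters.

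### The between-profile outlier rule does not name the calculation it screens; read naturally, it can remove a woman's pair from the paired t-test because of her exposure level, although her test/reference ratio is ordinary

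*SAP*

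**What the plan says.** SAP section 9.3.1, under Treatment of Outliers during Pharmacokinetic Analysis, has a part headed "Data between Individual Profiles". For six or more values, "an objective outlier test will be used to compare the atypical value to other values included in that calculation". The steps are:

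- "Transform all values in the calculation to the logarithmic domain".
- "Find the most extreme value from the arithmetic mean of the log transformed values and exclude that value from the dataset".
- Form mean ± 3 SD from the values that remain. If the omitted value lies outside, "then it is an outlier and will be excluded from analysis".
- Repeat, one value at a time, until nothing more is flagged.

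The preamble is softer. The procedure is optional, serves as justification for excluding data, and "does not require that the value be excluded from analysis". It adds: "The following methodology will not be used to exclude complete profiles from analysis". Results with and without the atypical value are promised only for fewer than six values. For larger sets, exclusions are documented in the final report, and approval of that report counts as approval of the exclusion.

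Section 9.3.2 analyses log AUC(0-τ) and log Cmax of NGM, NGMN and EE by a paired t-test, run separately by analyte and parameter, with the code line "paired test*ref".

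**The concern.** The outlier rule mentions neither pairing nor a test/reference ratio, and it leaves the calculation unnamed. Its heading and its first step point to single PK values compared across women. The paired t-test does not use a woman's level: it cancels, and only her log(test) − log(reference) remains. A woman with unusually high or low exposure in both periods can therefore be flagged although her ratio is unremarkable. Once one of her two values is excluded, the paired procedure has no difference for her in that analyte and parameter.

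Two things are at stake. First, two analysts could apply the rule to different quantities and remove different women from the main result of an open-label study. Second, if a few women truly have a strong interaction, their low test-period values are among those likely to be flagged. Excluding them pulls the estimate towards no interaction, which is the wrong direction for an interaction study.

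**Working it through.** **Inputs from the SAP.** 28 completers and a within-subject CV of 18.2% for EE AUC (section 7); the 3 SD leave-one-out steps (section 9.3.1); a paired analysis with a 90% CI (section 9.3.2).

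**Assumption.** The SAP gives no between-subject variability, so a log SD of 0.2, 0.4 and 0.6 is used.

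**Step 1: reproduce the SAP's precision.**
- Within-subject log SD: √ln(1 + 0.182²) = 0.1805.
- Expected half-width of the 90% CI: t(0.95, 27) × 0.1805 × √(2/28) = 1.703 × 0.1805 × 0.267 = 0.082.
- With 90% assurance: 0.082 × √(χ²(0.90, 27)/27) = 0.096, or 1 − exp(−0.096) = 9.1%.
- The SAP states 0.10 and 9.3%. With the CV taken directly as log SD and the assurance made conditional on coverage, the result is 9.3%. The base is sound and not in dispute.

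**Step 2: clean data.** Log value = woman's effect N(0, SD_b) + N(0, 0.1805) in each period, true ratio 1, 40,000 data sets per setting. The steps are iterated within each treatment, every flagged value is excluded, and incomplete pairs are dropped.

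| Between-subject log SD | Trials with a flag in either treatment | Mean pairs lost | Mean half-width | 90% CI coverage |
|---|---|---|---|---|
| 0.2 | 33% | 0.42 | 0.0810 | 89.0% |
| 0.4 | 30% | 0.38 | 0.0816 | 89.6% |
| 0.6 | 27% | 0.34 | 0.0818 | 89.7% |
| No exclusion | – | 0 | 0.0814–0.0815 | 90% |

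Of the test-treatment values flagged, 80%, 91% and 94% belong to pairs whose log ratio lies within 2 SD of the mean difference. This is a share of flagged values, not a rate per trial. Repeat runs put the flag rate at 26–33%.

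**Step 3: a true interaction in a few women (illustrative).** Each woman has a 5% chance of a true 60% reduction. The true geometric mean ratio is exp(0.05 × ln 0.4) = 0.955.

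| Between-subject log SD | No exclusion: ratio, coverage | Level screen: ratio, coverage | Ratio-scale screen: ratio, coverage |
|---|---|---|---|
| 0.2 | 0.955, 89% | 0.978, 81% | 0.983, 77% |
| 0.4 | 0.955, 89% | 0.963, 87% | 0.983, 77% |
| 0.6 | 0.955, 89% | 0.958, 89% | 0.982, 78% |

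**Step 4: the obvious alternative.** The same steps applied to each woman's log(test) − log(reference) flag a pair in 18–19% of clean trials. They shorten the mean half-width to 0.079 and lower coverage to about 88%. Step 3 shows that they also distort the estimate more than the level screen does.

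**The case against.** **The rule may already apply to ratios.** Because the calculation is not named, it could be the paired comparison, with test/reference ratios as the values to be logged. The text does not exclude this, so it does not establish that the screen is on the wrong scale. But the heading speaks of data between profiles, whereas a ratio combines two profiles. The level reading is the natural one, and the ambiguity itself needs removing. Nor are the values compared untransformed, as a reader might infer: the first step takes logs.

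**Exclusion is discretionary.** This is correct as far as the preamble goes, so lost pairs are possible rather than certain. The last step nevertheless says that an outlier is excluded. When the procedure is used, it is the stated justification, and at 28 pairs only documentation is promised.

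**A contradiction with the bar on excluding complete profiles.** A reader might infer one. It is not supported: removing one AUC leaves that woman's Cmax, tmax and other analytes in the analysis.

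**A serious loss of precision.** A reader might infer this too. The half-widths in step 2 show that it is practically nil.

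**Poor detection of a corrupted profile.** The level screen does find a one-period error less often than a ratio test when women differ widely. At a within-subject CV of 18.2% and a 3-fold error, it finds 85% against 88% at a between-subject CV of 20%, and 23% against 88% at 50%. The gap depends on a CV that the SAP does not give, and it vanishes when the two CVs are equal. A missed pair would also stay in with no screen at all, and the SAP has other routes: review of protocol deviations, and the within-profile rule with its with/without reporting. Better detection is a reason to examine unusual ratios. It does not justify deleting them automatically, as steps 3 and 4 show.

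**Conclusion.** The point holds in a limited form. The SAP does not name the calculation that the between-profile rule screens. On the natural reading, a woman's exposure level alone can take her pair out of the paired t-test for that analyte and parameter, and at the planned sample size the rule promises no with/without result.

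In clean data the practical harm is small: a flag in about 26–33% of trials per parameter, coverage of 89–90%, and almost no change in precision. It grows if a few women have a real, large interaction: in the illustration, the ratio moves from 0.955 to 0.958–0.978 and coverage falls to 81–89%, with the worst case at the smallest between-subject spread.

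These figures assume log-normal data, equal variance in both periods, 28 pairs, a within-subject CV of 18.2%, a between-subject log SD of 0.2–0.6, and exclusion of every flagged value. Since exclusion is optional, they are what the rule does when fully applied. A reader might conclude that the test should simply move to the within-woman ratio. The calculations do not support automatic exclusion on that scale, which selects women by the outcome being estimated.

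**What to change.** Add to the part of section 9.3.1 headed "Data between Individual Profiles", with a cross-reference in section 9.3.2:

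- *This screen applies to by-treatment descriptive summaries only.*
- *No AUC(0-τ) or Cmax value is removed from the paired t-test in section 9.3.2 on the basis of this statistical test alone.*
- *Any flagged value, and any unusual within-woman log(test) − log(reference), is examined for a cause, and the comparison is reported as a sensitivity analysis with and without that pair.*

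Do not substitute automatic exclusion on the ratio scale. Keeping all pairs in the main analysis restores the nominal 90% coverage in clean data. The cost is a few SAP sentences and, where something is flagged, one extra run of the paired t-test for that analyte and parameter.
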